Stool samples –

Efficient sampling

Protocol overview

Project title Stool samples - efficient sampling

Clinical trial design Proof of concept

Timetable November 2020 – December 2023

Purpose Testing of collection tubes for stool samples

Number of patients 50

Latest approval sep 14 2022

Summary

Several patients are admitted to the Oncology ward O81 and the medical department SUH, Køge (here primarily to rule out infectious diarrhea) with thin stools/diarrhea, which can be both chemo-induced and infectious and thus require isolation.

Patients who need to have a stool sample taken for microbiological examination risk receiving relevant treatment later if they cannot separate urine and stool. By waiting for a usable stool sample, the patient risks being hospitalized for a longer period of time and receiving relevant treatment with antibiotics or antidiarrheal agents later. In addition, there is a risk that any infection will be spread to other patients on the ward.

By developing a collection tube, the patient can have a stool sample taken upon arrival at the department and then receive relevant treatment when there is a response from the Microbiology Department. Resources can be saved on both isolation remedies and personnel if the patient is not diagnosed with a diagnosis requiring isolation.

In addition to the above, there is also the hygienic aspect that with the current remedies available, the staff must collect the stool sample from a basin and put it into a test tube that can be sent to the Microbiology Department. With the collection tube, it is possible to take the sample directly from the rectum.

With the completion of this study, it is expected that patients admitted with loose stools/diarrhea will be diagnosed more quickly and thus receive relevant treatment more quickly. This may lead to a shorter hospitalization period and savings on the resources that Zealand University Hospital uses on medicine, isolation measures and personnel.

The above method can be expected to be extended to other specialties than just oncology, as well as to the primary sector.

Background

Clinically, diarrhea is defined as three or more loose stools per day or an increased volume of stool (over 200 grams) per day. Diarrhea is divided into acute diarrhea, lasting less than two weeks, and chronic diarrhea, lasting more than two weeks. Diarrhea is defined based on the consistency, amount, appearance, and frequency of the stool [1]

Problem statement

Patients admitted with loose stools/diarrhea must be diagnosed quickly so that relevant treatment can be initiated. The current workflow of collecting stool samples from the pelvis without adding urine can extend the time to diagnosis and thus the hospitalization process, with the consequence that the patient will receive relevant treatment later.

Hypothesis

With a collection tube that can be easily inserted into the rectum, the time to collect the first usable stool sample will be shortened.

Purpose

Testing of collection tubes for stool samples.

Design

Proof of concept study, where the collection tube is tested on 50 hospitalized patients on Oncology Ward O81.

Inclusion criteria

- The patient must be at least 18 years old.
- The patient must be able to understand Danish
- All patients admitted to the Oncology ward O81 with loose stools/diarrhea. This is regardless of whether the patient is undergoing active medical cancer treatment and/or antibiotic treatment.
- It is a requirement that the patient is cognitively well-functioning and can understand the patient information related to the study.
- The patient must be able to cooperate optimally with the sampling itself. If this is not assessed at the time of admission, the patient will be excluded from the study.

Exclusion criteria

- Expected remaining life < 2 weeks

Recruitment

All patients admitted with loose stools/diarrhea will be offered the opportunity to participate in the study. They will be selected if they meet the inclusion criteria described above.

Procedures

Patients admitted with loose stools/diarrhea will have a stool sample taken with the collection tube at the time of admission.

The patient is placed on their side in a bed or on a stretcher before the actual sample collection.

The stool sample is then sent to the Microbiology Department for standard testing for Clostridium Difficile, pathogenic intestinal bacteria and viruses. No other analyses are performed and only the actual collection of the stool sample is included in the project. The stool sample taken with the collection tube replaces the stool sample with the standard method.

Method

In the current workflow for collecting stool samples, the patient must sign off with a stool sample on a basin. The stool must not be mixed with urine. The stool is then collected in a clear plastic container. A small spoon is attached to the brown lid of the plastic container and this is used to collect the stool in the plastic container. The lid is then screwed firmly onto the plastic container and it is marked with the patient's name and social security number from the PTB note. The plastic container is placed in the associated protective sleeve and sent for cultivation and resistance testing at the Microbiology Department.

If multiple samples are taken for the same examination, these must be taken from different stools, and if multiple samples are taken for different examinations, these can be taken from the same stool.

The method to be investigated in this study is the insertion of a collection tube into the rectum. The tube is passed 10 cm up the intestine. Then a spiral inside the collection tube is turned around and stool is collected in the tube, which is subsequently removed from the intestine again. The stool sample is now sealed inside the collection tube and the collection tube is marked with the patient's name and social security number from the PTB note. The collection tube is sent for culture and resistance determination at the Microbiology Department.

Experimental conditions: the subjects do not need to be specially prepared for the collection.

Microbiological analysis: cultivation and resistance testing of bacteria and viruses in stool samples. An amount of stool the size of a large pea or approximately 2 ml is used.

Static considerations

Since this is a proof -of -concept study and the results can only be divided into either successful or unsuccessful, 50 patients are considered a suitable number. No statistical calculation has been performed.

Timetable

Project start date: 01.11.20

Project end date: 31.06.23

Place

The study takes place at the Oncology Ward O81, Zealand University Hospital (SUH), Roskilde and the Medical Ward SUH, Køge.

Practical options

A patient room, bed or bed, collection tube, office facilities with access to the Health Platform must be used.

Rights

Nurse [name] will be responsible for collecting and storing data supervised by professor, senior physician [name].

Research engineer [name] will be responsible for the contact with the company that will produce the collection tube, and will be kept informed about the study.

Chief physician, clinical associate professor, PhD [name] will supervise the collection method itself and will be continuously informed about the study.

[name] will introduce nursing staff on the wards to the study so that they can participate to a certain extent in the collection of stool samples.

Ethics

It is estimated that there will be no additional inconvenience for patients who have a stool sample taken with the collection tube compared to the inconvenience of the standard method. There will be no additional attendances, as all patients are already hospitalized with diarrhea.

It will take less time to complete the questionnaire.

The study will be submitted to the Danish Medicines Agency, the Regional Scientific Ethics Committee and data notification to Region Zealand and will not be initiated until relevant approvals are available.

Information and consent

Patients included in the study will be informed verbally about the study at the time of admission and will be given written patient information about the purpose of the study. In this connection, the patient's immediate consent to participate in the study will be obtained.

The patient's consent gives the trial director, sponsor and sponsor's representatives, as well as any supervisory authority, direct access to obtain information in the patient's medical record, etc., including electronic medical records, in order to view information about the subject's health conditions, which is necessary as part of the implementation of the research project and for control purposes, including self-control, quality control and monitoring, which they are obliged to perform.

Data

Data is entered into Excel.

Data storage

Data is stored in pseudonymized form on PC, as all patients are assigned an allocation number. The allocation number ensures that no personally identifiable data is stored on PC. Backup files are placed in a locked filing cabinet in the department management office, and can be used to identify the patient.

Data will be stored in accordance with applicable regulations for trials, and destroyed thereafter.

The following patient data is collected:

Age, gender, cancer diagnosis, temperature (> 38.5), neutrophil count ($< 0.5 \times 10^9 /l$), number of bowel movements in the last 24 hours, possible constipation in the last 24 hours, date of last series and type of medical cancer treatment (if applicable), date of hospitalization, date of stool sample and results of stool sample.

The above patient record information must be used to ensure that these are relevant patients in terms of being hospitalized with infectious diarrhea, as well as to describe demographics and any comorbidity.

The information that will be used in the project before consent is given from the subjects is passed on to the researcher.

The experiment has been registered with Region Zealand and is subject to the Data Protection Act and the General Data Protection Regulation .

Economy

The study is supported by the Department of Clinical Oncology and the Innovation and Technology Council at Zealand University Hospital with Match Point funding of DKK 100,000.

MatchPoint is a project under Zealand University Hospital, where innovation projects, after a professional assessment, are financially supported with DKK 100,000 for development and testing.

MatchPoint funds: DKK 100,000.

The above has financed the development of collection tubes, patent search and salaries.

Funding: the experimental group has received an Inno Explorer grant, funding the study.

There are no affiliations with any companies with an interest in the trial, among any of the participants in the trial group. The study is part of a product development, and there is no product on the market at present. A number of prototypes will be manufactured, paid for by the trial group, with funds from MatchPoint allocated to the group.

The research group has no financial interest in the study, but wishes to patent the invention.

Recruitment of subjects and informed consent

The subjects are recruited at the time of admission when the doctor records the admission record and prescribes that stool samples be taken for culture and resistance testing. The patient will be isolated and will thus be alone in a patient room, so that oral information and conversation about the study and its rationale can take place undisturbed. Written patient information will be provided.

The right to an assistant will be offered when a potential candidate for the study is identified.

Since the purpose of the study is a quick and efficient collection of stool from the rectum, where we have the opportunity to reduce the time in isolation, we want the reflection time to be reduced as much as possible, preferably to 1-2 hours, and since the experiment is considered completely harmless and will not impair treatment, this is considered reasonable.

The patient's immediate consent to participate in the study is obtained as soon as a prescription from a doctor is available and the patient has given his consent after a period of reflection.

Publication of results

As it is a proof of concept study, the results will be used to develop a larger study.

Trial results of both positive, negative and inconclusive grades will be published.

Administrative matters

- Notification/approval to the Danish Medicines Agency
- Notification/approval to the Regional Research Ethics Committee
- Data notification/approval to Region Zealand
- Security
- Insurance: Patients are covered by the hospital's general patient insurance.
- Division of responsibilities
- Publication – journal

Reference list

Fernández-Bañares F. et al: *æ*Chronic diarrhoea : Definition, classification and diagnosis. Elsevier, Gastroenterol Hepatol . 2016;39(8): 535-559

Layman's summary

The purpose of this study is to collect a stool sample from the patient who is admitted with loose stools/diarrhea, already at the time of admission.

The study is not considered to be associated with any risks or disadvantages for the patients who participate.

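### The only hypothesis is a comparative claim about time, but the design has one group, no standard-method reference and a success/failure result, so it cannot be tested

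*Protocol*

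**What the plan says.** - **Hypothesis.** The section contains one statement: with an easily inserted tube, "the time to collect the first usable stool sample will be shortened".
- **Summary.** Completing the study is expected to lead to quicker diagnosis and treatment for patients admitted with diarrhoea.
- **Design.** "Proof of concept study, where the collection tube is tested on 50 hospitalized patients on Oncology Ward O81". No second group is described.
- **Procedures.** "The stool sample taken with the collection tube replaces the stool sample with the standard method". The same section narrows the scope: "only the actual collection of the stool sample is included in the project".
- **Method.** The basin workflow is described step by step, but no time to a usable sample is given for it and no historical or record-based reference is named. On quantity it says: "An amount of stool the size of a large pea or approximately 2 ml is used".
- **Static considerations.** The outcome is binary: "the results can only be divided into either successful or unsuccessful". The number 50 is called suitable, and the section states that no calculation was made.
- **Data storage.** The listed items related to timing and outcome are "date of hospitalization, date of stool sample and results of stool sample".
- **Publication of results.** The results are to feed into a larger study, and positive, negative and inconclusive results will all be published.

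**The concern.** The word *shortened* requires a duration, and something for that duration to be shorter than. The protocol declares a result that is not a duration, and it leaves no patient or reference value from which the standard-method duration could be learned. An analysis plan could define terms and choose methods, but it could not test this hypothesis without adding a comparator and departing from the statement that results are only successes or failures.

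What is at stake is the conclusion. The time hypothesis is the only one on record and the Summary repeats the expectation of faster diagnosis. A high success proportion could therefore easily be written up as evidence that time was saved. The labels positive, negative and inconclusive, which the protocol promises to publish under, would also have no basis for this hypothesis.

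**Working it through.** **1. The plan's own figure.** The sample size is 50. The protocol gives no alpha, power, effect size, rate or standard deviation and says no calculation was made, so there is nothing to reproduce.

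**2. What the hypothesis needs.** Write T_tube and T_std for the time to the first usable sample under each method. The hypothesis concerns a contrast such as θ = median(T_std) − median(T_tube), with the claim θ > 0. Each possible source of information on T_std can be checked against the protocol:

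| Possible source | What the protocol provides |
|---|---|
| Concurrent group | None; the tube is used in all 50 patients (Design) |
| Same patient, both methods | Ruled out; the tube sample replaces the standard one (Procedures) |
| Historical or record-based group | None named |
| Fixed reference time | None given; Method describes the workflow only |

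T_std is therefore not observed and is not set to a constant, so θ cannot be estimated.

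**3. What is known about T_tube.** The declared result is binary, so time is not the outcome. The dates listed under Data storage would allow a crude interval in days for tube patients. That interval would have nothing to be compared with. It would also be largely fixed by the procedure itself, because sampling is scheduled at admission and follows a consent step for which "we want the reflection time to be reduced as much as possible, preferably to 1-2 hours".

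**4. What the design can estimate.** Let X be the number of successes among n = 50. The exact (Clopper-Pearson) 95% interval for the success probability p is:

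- lower limit = the 0.025 quantile of Beta(x, n − x + 1)
- upper limit = the 0.975 quantile of Beta(x + 1, n − x)

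The counts below are illustrative and not taken from the protocol:

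| Successes | Proportion | Lower limit | Upper limit | 95% CI |
|---|---|---|---|---|
| 40/50 | 80% | Beta(40, 11) → 0.663 | Beta(41, 10) → 0.900 | 66% to 90% |
| 45/50 | 90% | Beta(45, 6) → 0.782 | Beta(46, 5) → 0.967 | 78% to 97% |

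**5. Link between the two.** Nothing in p determines θ. A result of 45/50 is compatible with the standard method being slower, equally fast or faster. However good the success proportion, it does not bear on the hypothesis as worded.

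**The case against.** The strongest reply is that this is a proof-of-concept study. Its stated purpose is to test the tube, its scope is limited to collection, and its results are to inform a larger study. On that reading the time statement is the rationale for the whole programme, and a single group with a binary outcome is adequate. Much of this stands: the design is sound for that purpose and nothing here calls for a second arm. It does not remove the mismatch, because the time claim stands under its own Hypothesis heading, no other hypothesis is offered, and the Summary ties the expected gain in speed to completion of this study.

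A reader might infer two stronger points that the documents do not support.

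- **That the success criterion, the number of attempts and the usability of the sample are missing from the plan.** These are commonly settled in an analysis plan or case report form, which are not shown. Ethics also mentions a questionnaire whose content is not given. The record information under Data storage is described as serving to confirm that patients are relevant and to describe them, so the list need not be the full outcome dataset. The results item may itself show whether a sample could be analysed.
- **That recording dates rather than clock times would hide a real gain, by a calculable amount.** The protocol gives no collection times and no comparison group. Any power figure would rest wholly on assumed medians, spread and group sizes, and would shift with the treatment of the reflection period.

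**Conclusion.** The point holds as a mismatch between hypothesis and design. The single stated hypothesis cannot be tested by this trial, and this follows from the protocol's own statements without any numerical assumption. The trial can deliver a one-group success proportion, with a 95% interval of roughly 66% to 90% at 40/50 or 78% to 97% at 45/50; those counts are the only assumed inputs. The test of the tube remains valid for its stated purpose. What does not follow is any statement that time was shortened or diagnosis was faster. The protocol should be corrected on this point, but the correction is modest and the design need not change.

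**What to change.** **Main change.**

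1. Restate the hypothesis as feasibility with one success criterion, for example: *the first tube collection yields a sample on which Microbiology can carry out the ordered standard analysis*.
2. Report it as a proportion of all patients in whom collection is attempted, with failed attempts counted as unsuccessful, and give an exact 95% confidence interval.
3. State in the Hypothesis and the Summary that shortened time and faster diagnosis are questions for the larger study mentioned under Publication of results.

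**Suggestion only.** Make sure that the number of attempts and whether the sample could be analysed (yes/no) are recorded, if the questionnaire or case report form does not already cover them.

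**If the time hypothesis is kept instead.** Name a standard-method reference, record clock times for both methods, and label the comparison as non-randomised.

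**Cost.** The main change costs wording and at most two simple data items. It adds no patients and no patient procedures. Keeping the time hypothesis would cost more, because reference data would have to be obtained.

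### A known neutrophil count below 0.5 × 10^9/l does not stop insertion of the prototype tube, yet the protocol rules out any harm and shortens reflection time partly on that ground

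*Protocol*

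**What the plan says.** **Who is eligible.** Under Exclusion criteria the Protocol lists only "Expected remaining life < 2 weeks". The Inclusion criteria cover age, language, admission to the oncology ward with diarrhea, cognition and cooperation. On treatment they add: "This is regardless of whether the patient is undergoing active medical cancer treatment and/or antibiotic treatment". Recruitment selects patients on these inclusion criteria.

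**What is done.** Procedures states: "Patients admitted with loose stools/diarrhea will have a stool sample taken with the collection tube at the time of admission". Method states: "The tube is passed 10 cm up the intestine". A spiral inside the tube is then turned to collect stool. No special preparation is needed. Economy says that nothing is yet on the market and that prototypes will be made.

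**What is known about neutrophils.** The data list under Data storage includes "temperature (> 38.5), neutrophil count", the latter with the limit < 0.5 × 10^9/l, together with the date of the last treatment series. On the use of these data, the section says that they "must be used to ensure that these are relevant patients in terms of being hospitalized with infectious diarrhea, as well as to describe demographics"; comorbidity is to be described too. A further sentence there suggests that some record information reaches the researcher before consent.

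**What is said about risk.** Recruitment of subjects and informed consent treats the experiment as wholly without harm, and gives this as one reason for a reflection time of preferably 1-2 hours. The Layman's summary says that no risk or disadvantage is expected. Neither statement mentions neutropenic patients.

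**The concern.** The protocol singles out severe neutropenia by its own cut-off and foresees that some participants will have it, but attaches no action to it. A nurse or doctor who follows the text exactly would insert the tube in a patient whose count is known to be below 0.5 × 10^9/l.

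What is at stake is patient safety. A rectal insertion can cause a small injury through which gut bacteria enter, and a severely neutropenic patient has little defence against them. This is general clinical judgment and is not stated in the documents. The basin method puts nothing into the rectum, so this particular risk comes with the study procedure.

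Consent is affected too. The unqualified safety statement helps to justify a short reflection time, and it is least secure for exactly these patients.

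**Working it through.** The protocol states no figure on this point, so there is nothing to reproduce. The check is mainly one of text.

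**Step 1: could any criterion stop the insertion?** The one exclusion concerns life expectancy. None of the inclusion criteria is a blood count or a bowel-safety check; the cooperation criterion concerns the patient's ability to take part in the sampling. Result: no.

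**Step 2: does the data list act as a check?** Its stated purposes are relevance to infectious diarrhea and description. A low count does not make a patient less relevant, so applying this use would not keep the patient out. The count may well be seen before insertion, but no consequence follows from seeing it. Result: no.

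**Step 3: does oversight act as a check?** A doctor prescribes the stool sample (Recruitment of subjects and informed consent), and a chief physician supervises the collection method (Rights). The first is an order for a stool test and the second concerns technique. Neither is tied to a patient's neutrophil count. Result: no.

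**Step 4: is the safety statement supported?** Ethics compares only inconvenience with the standard method. The protocol cites no safety data for the tube. Result: the statement is an assertion.

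**Step 5: exposure, under assumption only.** The share p of patients below the limit is not given. With n = 50 from the protocol:

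| Assumed p | Expected insertions below the limit, 50 × p | Chance of at least one, 1 − (1 − p)^50 | Otherwise eligible patients needed for 50 tube samples if excluded, 50/(1 − p), rounded up |
|---|---|---|---|
| 2% | 1 | 0.636 | 51.02 → 52 |
| 10% | 5 | 0.995 | 55.6 → 56 |
| 30% | 15 | > 0.999 | 71.4 → 72 |

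These figures describe exposure and recruitment. They are not probabilities of harm.

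**Step 6: could the study show afterwards that the tube is harmless in this group?** With no harms among m patients, the exact one-sided 95% upper limit for the harm rate is 1 − 0.05^(1/m).

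- All 50 patients: 1 − 0.05^(1/50) = 5.8%.
- 15 neutropenic patients (p = 30%): 1 − 0.05^(1/15) = 18%.
- 5 neutropenic patients (p = 10%): 1 − 0.05^(1/5) = 45%.

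A clean result would therefore say little about this group, and the safeguard has to be set beforehand.

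**The case against.** **The harm premise lies outside the documents.** This stands. No harm rate is given, and the size of the risk cannot be argued from the text. The gap does not depend on a rate: an invasive prototype, a vulnerable group that the protocol itself identifies, no rule for that group, and an absolute safety statement.

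**The broad eligibility is deliberate.** The Summary and Problem statement say that waiting for a usable sample delays treatment and can prolong the stay. Severely neutropenic patients may be among those for whom delay matters most. This also stands, as a cost of exclusion. But the protocol does not weigh delay against insertion risk; it assumes that the second is nil. An excluded patient receives today's standard method.

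**Oversight exists.** Prescription, supervision and the required approvals mean that insertion is not unsupervised. Device risk documents and the patient information are not at hand and may say more. Even so, a patient-level eligibility rule belongs in the protocol.

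**Stronger readings that the documents do not support.** A reader might take the exposure percentages as a risk of injury or infection; they only restate an assumed share. A reader might also infer that staff will not know the count before insertion. The protocol does not say so, and its sentence on information before consent points the other way. The defect is that a known count has no consequence.

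**Conclusion.** The point holds as a gap in the safety rules together with an overstated safety claim. As written, a known neutrophil count below 0.5 × 10^9/l does not stop a 10 cm rectal insertion of a prototype, and an unsupported statement of harmlessness is used to shorten reflection time. The sponsor should correct both; confidence is medium because the size of the harm is unknown.

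The conclusion rests on the clinical judgment that severe neutropenia raises the infection risk of rectal insertion. No harm rate is claimed. The number of patients concerned depends wholly on an assumed share, illustrated above at 2% to 30%.

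One related matter needs confirmation. The Inclusion criteria and Design name only Ward O81, whereas Place says "The study takes place at the Oncology Ward O81, Zealand University Hospital (SUH), Roskilde and the Medical Ward SUH, Køge". Whether Køge patients are eligible affects how many participants would lack a recent count, but not the conclusion for oncology patients.

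**What to change.** 1. Add to the Exclusion criteria: *Neutrophil count < 0.5 × 10^9/l measured during this admission or in the 48 hours before it.* For patients on active medical cancer treatment or with a recent series, such a count must be available, and the prescribing doctor checks and records it before insertion. The sponsor sets the window for a recent series and confirms the 48 hours, which are a proposal. Other patients need no extra blood test.
2. Sample excluded patients by the standard basin method. They do not count toward the 50 or as unsuccessful samples, and their number is reported.
3. In Recruitment of subjects and informed consent and in the Layman's summary, delete the claims of no harm and no risk. Say instead that rectal insertion of a prototype carries a possible risk of discomfort, minor injury or infection whose size is not known. Calling the tube low risk would be another unsupported assurance. Change the patient information too if it uses the same wording.
4. Confirm whether Køge patients are eligible.

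**Cost.** An amendment to the criteria and risk wording, a recorded check by the doctor, and a tally of excluded patients. The count and the date of the last series are already on the data list. Some patients will wait for a blood result, partly within the reflection time; laboratory turnaround is not given. Excluded patients keep today's basin delay. Recruitment is somewhat slower (52, 56 or 72 otherwise eligible patients for 50 tube samples under the assumed shares), and the study yields no tube data in severely neutropenic patients.

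### The only hypothesis is a shortened time to a usable stool sample, but the plan describes no comparator, a success-or-failure result and, for timing, two calendar dates, so it cannot support that conclusion

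*Protocol*

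**What the plan says.** The protocol's Hypothesis section makes one claim: with the tube, "the time to collect the first usable stool sample will be shortened". Under Procedures, patients "will have a stool sample taken with the collection tube at the time of admission", and then: "The stool sample taken with the collection tube replaces the stool sample with the standard method". No group or period sampled by the basin method is described as a comparison.

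Static considerations justifies the 50 patients on the ground that "the results can only be divided into either successful or unsuccessful", and states that no calculation was made.

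Under Data storage, a list opens with "The following patient data is collected". Its items bearing on this interval are "date of hospitalization, date of stool sample and results of stool sample". The list has no clock time, and no date or time for the doctor's order or for consent. The text after it gives its use: "The above patient record information must be used to ensure that these are relevant patients", and to describe demographics and comorbidity.

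Recruitment of subjects and informed consent places consent after the doctor's prescription and a reflection time of preferably 1-2 hours. Publication of results says that the findings will serve to develop a larger study.

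**The concern.** The hypothesis is comparative and concerns time. The design has one arm, the result is binary, and the listed timing data are dates. These do not fit together. If most tube samples succeed, a reader of the report could take the hypothesis as confirmed, although a success proportion says nothing about whether time was saved.

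The larger study is the second thing at stake. To plan it, one would want to know how many hours the tube takes from order to sample, and how much of that is the consent process, which would not be part of routine use. Followed as written, the plan hands on a success proportion and the share of patients sampled on the day of admission. An analysis plan written later cannot recover times that nobody recorded.

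**Working it through.** The protocol gives no alpha, power, effect size or standard deviation for the 50 patients, so there is no figure to reproduce. The check is whether the planned data can carry the stated claim.

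**Step 1: what the claim needs, against what is planned.** To conclude that a time is shortened one needs:

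- The time with the tube for each patient. Planned: two dates in the data list (Data storage).
- The time with the standard method in comparable patients. Planned: none described, since the tube sample replaces the standard one (Procedures).
- A result expressed as time. Planned: success or failure (Static considerations).

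The second item decides the matter. Exact tube times would complete the first item and leave the second empty.

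**Step 2: what two dates can show.** Let *a* be the clock hour of admission (0 ≤ *a* < 24) and *T* the true delay to the sample in hours. The recorded difference in days is

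D = floor((a + T) / 24).

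- D = 0 requires T < 24 − a. As *a* may be as low as 0, D = 0 fits any T from 0 to just under 24 h.
- D = 1 requires 24 − a ≤ T < 48 − a. Over all *a*, this fits any T above 0 to just under 48 h.

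Examples with chosen hours, for illustration only:

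- Admission 08:00, T = 2 h: floor(10/24) = 0 days.
- Admission 08:00, T = 12 h: floor(20/24) = 0 days.
- Admission 23:00, T = 2 h: floor(25/24) = 1 day.

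Delays of 2 h and 12 h can be recorded alike, and the same 2 h delay can be recorded as 0 or as 1 day. This follows from the definition of a date and needs no assumption about when patients arrive.

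**Step 3: the trial's own delay.** Let R be the time from order to consent and C the time from consent to sample. The order-to-sample time is R + C. The protocol wants the reflection time, which falls within R, to be 1-2 h. Neither the order nor the consent is in the data list, so R, C and their sum cannot be computed from the listed items.

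**The case against.** The strongest reply is that this is a proof-of-concept test of a device. The stated purpose is to test collection tubes, the result is openly binary, and the data list exists to confirm eligibility and describe the patients. On that view the hypothesis is motivation and nobody intends to test it. Much of this stands: the success proportion and the 50 patients are unaffected by the point. But the sentence is labelled as the hypothesis and is the only one, so it should match what the study can show.

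Three stronger readings are tempting, and the documents do not support them.

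- A reader might infer that sampling times will not be captured at all. Under Information and consent, access to the electronic medical record is provided for, and Practical options requires access to the hospital's record system. Ethics says "It will take less time to complete the questionnaire" without describing what the questionnaire holds. What can be said is that the protocol names no clock times.
- A reader might infer that the coarse dates are what defeats the hypothesis, and that clock times would rescue it. They would not, because there would still be no comparator.
- A reader might infer that the dates are worthless. They show whether the sample was taken on the day of admission. The Summary describes the harm of waiting without a unit, so if standard collection takes days, whole-day differences carry some information. The 1-2 hours is a wish about reflection time and not a target for sampling.

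It is also fair that no section sets out to describe the consent delay. Recording it helps to plan the larger study; leaving it out contradicts nothing.

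**Conclusion.** The point holds in this form: as written, the plan cannot support its only hypothesis. The main reason is that no comparator is described. The binary result and the date-only timing list add to it. The listed data give no time in hours, since a same-day pair of dates covers everything from 0 to just under 24 h.

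The consequence is limited. The sample size and the success proportion stand. What is lost is the claim of a shortened time and, unless the times are captured elsewhere, a description of tube sampling time for the larger study. This is worth correcting but does not invalidate the trial.

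The conclusion assumes that a date in the list means a calendar date without a time, and that no comparison with basin-sampled patients is planned outside this protocol. If the record or the questionnaire already supplies the clock times, the part about timing reduces to listing them; the part about the comparator remains.

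**What to change.** 1. Restate the hypothesis and the intended conclusion as the proportion of patients with a usable tube sample, plus a description of time in the tube group. Do not present the results as evidence that time is shortened.
2. Keep the two dates and add clock times to the data list for three events: the doctor's stool-sample order, consent, and tube sample obtained. If the questionnaire or the record already captures them, name the source in the protocol instead.
3. Report order-to-sample and consent-to-sample times descriptively. Keep patients without a usable tube sample in the denominator, with their time given as not reached, so that the description is not confined to successes. Do not let the time of a later basin sample stand in for the tube's time.

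The cost is three clock-time columns in Excel and brief charting at the bedside, with no extra patients or procedures. The sponsor gives up the claim of a shortened time. The gain is descriptive and serves the planning of the larger study; it supplies no comparison with the basin method.
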